The usual first treatment for NMIBC (Ta, T1, and CIS) is transurethral resection of the bladder tumors (TURBT), followed by intravesical immunotherapy, most commonly with bacillus Calmette-Guérin (BCG). ([Babjuk 2013, American Urological Association 2014](#)) In patients with T1 tumors, a second TURBT is recommended. ([Babjuk 2013, American Urological Association 2014](#)) Induction therapy with BCG is usually dosed as 6 once-weekly instillations. ([Babjuk 2013, American Urological Association 2014](#)) In patients with high-grade Ta, T1, and CIS, maintenance therapy with BCG of at least 1 year is recommended, ([Babjuk 2013, Anastasiadis 2012](#)) although the optimal dose, dosing schedule, and duration of treatment are unknown. ([American Urological Association 2014](#)). Local and systemic side effects are common with intravesical BCG therapy, causing discontinuation of treatment in approximately 20% of patients. ([Sylvester 2011](#)) Approximately 75% of patients experience local side effects (including cystitis, irritative voiding symptoms, and hematuria), while 40% report systemic side effects, including general malaise and fever. ([Sylvester 2011](#)) Intravesical BCG failure occurs in up to 40% of patients. ([Sylvester 2011](#)) Because of the high risk for development of muscle invasive disease, cystectomy is recommended for CIS and high-grade Ta and T1 patients who experience disease recurrence following intravesical therapy. ([Babjuk, 2013, American Urological Association 2014](#)) For patients unable or unwilling to undergo cystectomy, treatment options are limited.

Vicinium™ (Vicinium) contains the active pharmaceutical ingredient VB4-845, which is a recombinant fusion protein produced in *Escherichia coli* (*E. coli*) that expresses a humanized single-chain antibody fragment (scFv) specific for the epithelial cell adhesion molecule (EpCAM) antigen linked to ETA(252-608). ETA(252-608), which is a truncated form of *Pseudomonas* exotoxin A (ETA) that lacks the cell binding domain, is a single polypeptide fusion protein produced by continuous translation of a single construct.

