### **14.3 Protocol-Defined Events in the Analysis of Event-Free Survival**

Event-free survival (EFS) will be determined for all treated subjects (See [Section 17](#)). Events in the analysis of EFS include:

- Treatment failure as defined in [Section 14.2](#)
- Death (as a first event)

Subjects without evidence of a treatment failure who are diagnosed with upper or lower urinary tract urothelial carcinoma by histology, cytology or radiographic evidence as their first event will be censored in the analysis of EFS at the date of diagnosis.

Subjects without evidence of a treatment failure who undergo cystectomy will be censored in the analysis of EFS at the date of cystectomy.

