To evaluate biomarkers that may be associated with response or disease progression or treatment failure, which may include, for example, EpCAM status, tumor subtype morphology, furin levels in tumor cell endosomes, presence of a glycosaminoglycan coat, and presence of receptors that could impede a host anti-tumor immune response such as PD-L1.

3. **GENERAL STATISTICAL CONSIDERATIONS**

3.1. **SAMPLE SIZE AND POWER**

Assuming the true complete response rate at 12 months is 30%, sample sizes associated with various widths of a two-sided, exact (Clopper-Pearson) 95% confidence intervals are provided in the table below:

Sample Size (N)	Target Distance from P to Lower Limit	Proportion (P)	Lower Limit
121	0.080	0.300	0.220
95	0.090	0.300	0.210
76	0.100	0.300	0.200

Under the provided assumptions, a sample size of ≥ 77 evaluable subjects with early relapsed/refractory CIS with or without papillary disease is sufficient to estimate complete response rate with an exact 95% confidence interval that excludes 0.2 (PASS 2008).

The secondary endpoint of event-free survival (EFS) will be used to assess the treatment effect in all subjects, i.e., those with CIS (with or without papillary disease) and those with papillary-only disease. An estimate of EFS at the 18 month time-point will be calculated. The total sample size of 134 subjects will provide at least 80% power to test the null hypothesis that the event-free survival rate at 18 months is 20% versus the alternative hypothesis that the event-free survival rate at 18 months is $\geq 30\%$. This calculation is based on the assumptions of a nonparametric distribution for event-free survival and the length of follow-up is 24 months.

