EFS is defined as the interval from the date of first dose of study treatment to an event. Subjects who have a treatment failure or die following the post induction visit will be treated as having an event on the date of treatment failure or death. Subjects without evidence of a treatment failure who are diagnosed with upper or lower urinary tract urothelial carcinoma by histology, cytology or radiographic evidence will be censored at the date of diagnosis. Subjects without evidence of a treatment failure who undergo cystectomy will be censored at the date of cystectomy. All other subjects will be censored at the time of last assessment including long-term follow up.

Censoring rules for the analysis of EFS are presented in the table below.

Table: Censoring scheme for EFS

Situation	Date of Event or Censoring	Outcome
Treatment failure	Date of treatment failure	Event
Death without treatment failure and occurring prior to treatment discontinuation	Date of death	Event
Death without treatment failure and occurring after treatment discontinuation	Date of last evaluable disease assessment on or prior to treatment discontinuation ^a	Censored ^a
No baseline disease assessment	Date of first dose	Censored
No on-study disease assessments and no death	Date of first dose	Censored
No treatment failure and no death	Date of last evaluable disease assessment	Censored
New anti-cancer therapy received without treatment failure and reported prior to or on the same day as disease assessment	Date of last evaluable disease assessment on or prior to the date of initiation of subsequent therapy	Censored
Second non-NMIBC cancer reported prior to or on the same day as disease assessment	Date of last evaluable disease assessment on or prior to the date of diagnosis of non-NMIBC cancer	Censored
a This censoring rule acknowledges that disease assessments were not recorded after treatment discontinuation due to an AE.		

Cystectomy-Free Days

Cystectomy-free days is defined as the time from the date of first dose of study treatment to physical removal of the bladder. Subjects who are alive and do not have their bladder removed will be censored at the time of last contact.

Censoring rules for the analysis of cystectomy-free days are presented in the table below.

Table: Censoring scheme for Cystectomy

Situation	Date of Event or Censoring	Outcome
Cystectomy	Date of cystectomy	Event
Death without cystectomy	Date of death	Censored
No cystectomy	Date of last contact	Censored

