5. STATISTICAL METHODS

Descriptive statistical methods will be used to summarize the data from this study, with hypothesis testing performed for the primary and other selected efficacy endpoints. Unless stated otherwise, the term “descriptive statistics” refers to number of subjects (n), mean, median, standard deviation (SD), minimum, and maximum for continuous data and frequencies and percentages for categorical data.

All data collected during the study will be included in data listings. Unless otherwise noted, the data will be sorted first by subject number and then by phase (induction, maintenance), cycle/visit, and date.

Unless otherwise specified, all statistical testing will be two-sided, and will be performed using a significance (alpha) level of 0.05.

The statistical analyses will be conducted with the SAS® software package version 9.2 or higher. All analyses will be subject to formal verification procedures. Specifically, results will be verified utilizing independent programming prior to issuance of the draft statistical report. All documents will be verified by the lead statistician to ensure accuracy and consistency of analyses.

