5.2. EFFICACY ANALYSIS

5.2.1. Primary Efficacy Endpoint

The primary outcome measure is the complete response rate in subjects with refractory /relapsed CIS or CIS plus papillary disease (i.e., cohorts 1 and 2) following the initiation of Vicinium therapy.

Patients who discontinue or die before Month 3 will be included in the denominator of the primary analysis.

For the primary efficacy endpoint analysis, the following conventions will be utilized in determining treatment failure or complete response at a given visit.

1. Subjects that have centrally read pathology findings ('CIS', 'any-grade T1', 'high-grade Ta') or centrally read cytology results ('High Grade Urothelial Carcinoma') that indicate treatment failure for a given visit will be considered to have treatment failure.
2. Subjects who met a treatment failure criterion at a previous visit are treatment failures at all subsequent visits.
3. Subjects who have discontinued the study on or prior to the visit and have missing data that would be necessary to generate response are considered non-CRs.
4. Subjects who do not meet criterion 1-3 are complete responders.

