7. CHANGES IN THE PLANNED ANALYSES

Based on FDA Guidance an analysis of Cohort 1 + Cohort 2 is now planned as the primary efficacy population. In particular, the FDA has stated that recurrence of bladder cancer within 12 months of BCG is an acceptable study population for investigational agents in this setting.

No other changes to the protocol planned analyses have been described. Should changes arise, these changes will be fully described in the Clinical Study Report.

Following the completion of the protocol-specified analyses, the sponsor may choose to conduct additional exploratory analyses. Such analyses will be detailed in a separate document.

8. **REVISION HISTORY**

Date	Revision	Rationale
27OCT2020	Updated Section 3.3.8 by study visit windows for maintenance month and long-term follow-up windows	Updated for 3 months to cover 91 days (i.e. 13 weeks) instead of 12 weeks for consistency with response assessments which occur every 13 weeks during maintenance.
27OCT2020	Removed third sensitivity analysis for efficacy endpoints	Data collection did not allow for determination of upper and lower tract disease.

9. **PROGRAMMING CONVENTIONS**

- Page orientation, margins, and fonts: Summary tables, listings, and figures will appear in landscape orientation. There should be a minimum of a 1.25" boundary on the upper (bound) edge, and a minimum of a 1.0" boundary on the remaining three edges. Output should be printed in Courier New with a point size of 8. Titles may be printed using a larger font (e.g., Arial point size 10).
- Identification of analysis population: Every summary table and figure should clearly specify the analysis population being summarized. Listings will be prepared for all enrolled subjects.
- Group headers: In the summary tables, the group headers will identify the cohort and the within-group sample size for the indicated analysis population. Of note, the header's sample size does not necessarily equal the number of subjects actually summarized within any given summary module; some subjects in the analysis population may have missing values and thus may not be summarized.
- Suppression of percentages corresponding to null categories: When count data are presented as category frequencies and corresponding percentages, the percent should be suppressed when the count is zero in order to draw attention to the non-zero counts.

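### 18-month event-free survival censors subjects at cystectomy and at tract carcinoma, which may bias it upward, and no EFS sensitivity analysis tests this

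*SAP*

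**What the plan says.** SAP 3.3.7 defines an EFS event as treatment failure or death up to treatment discontinuation, and states that neither cystectomy nor upper or lower tract urothelial carcinoma is an event. For cystectomy the rule reads "Subjects without evidence of a treatment failure who undergo cystectomy will be censored at the date of cystectomy"; for tract carcinoma the censoring date is the date of diagnosis. SAP 5.2.5 repeats both rules. Protocol 14.3 and 17.5 agree: such a subject "will be censored in the analysis of EFS at the date of cystectomy". The EFS censoring table in SAP 3.3.7 has no row that names either exit.

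SAP 3.1 attaches a hypothesis and power to 18-month EFS: "The total sample size of 134 subjects will provide at least 80% power", against a null stated as "the null hypothesis that the event-free survival rate at 18 months is 20" percent and an alternative of at least 30%. SAP section 5 sets the default that "all statistical testing will be two-sided, and will be performed using a significance (alpha) level of 0.05". SAP 5.2.5 plans a Kaplan-Meier estimate with a 95% confidence interval at 18 months.

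SAP 5.2.3 plans two sensitivity analyses, both for the primary complete response analysis. In the list of final tables (SAP section 12) these appear for complete response and duration of response. EFS is repeated only by population and subgroup.

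On tract disease, SAP section 8 records that a third sensitivity analysis was removed because "Data collection did not allow for determination of upper and lower tract disease".

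**The concern.** Kaplan-Meier censoring assumes that a subject censored on a given day had the same outlook as those still followed. Cystectomy and tract carcinoma may not meet that assumption. The protocol's Introduction says that "cystectomy is recommended for CIS and high-grade Ta and T1 patients who experience disease recurrence following intravesical therapy", so the operation is tied to the course of the disease. Tract carcinoma is itself urothelial cancer, and Protocol 11.3 lists it, like cystectomy, as a reason to stop study drug. Cystectomy also ends the 13-week disease evaluations (Protocol section 14), so later data cannot settle whether the subject would have failed.

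If subjects leave by these routes because their disease is going badly, the censored curve stays too high. What is at stake is the estimate set against a 20% null, and whether its lower confidence limit clears 20%. The plan offers no second estimate by which a reader could judge this.

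The tract rule raises a separate question. SAP 3.3.7 exempts subjects with tract malignancy from treatment failure and censors them in EFS, although section 8 says tract disease could not be determined from the data collected.

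**Working it through.** **Step 1: the plan's own figure.** Inputs from SAP 3.1 and section 5: N = 134, null 20%, alternative 30%, two-sided alpha 0.05. For a one-sample test of a proportion, with null variance under the null and alternative variance under the alternative:

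power = Φ{[(0.30 − 0.20) − 1.96 × √(0.2 × 0.8/134)] / √(0.3 × 0.7/134)} = Φ{(0.1000 − 0.0677)/0.0396} = Φ(0.815) = 79.3%.

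This is close to the stated 80%. The calculation makes no allowance for either exit. The difference it is built on is 10 points.

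**Step 2: size if cystectomies count as events.** The documents give no rate, so the following are assumptions: 134 subjects; EFS 45% at the first evaluation and 30% at 18 months; visits every 91 days; and 3, 7 or 13 cystectomies without documented failure between months 3 and 15 (about 2%, 5% and 10% of 134). Simulation with 1,500 replicates, Kaplan-Meier read at Day 548:

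| Cystectomies | EFS, censored | EFS, counted as events | Gap (points) |
|---|---|---|---|
| 3 | 29.9% | 28.2% | 1.7 |
| 7 | 29.9% | 26.0% | 3.9 |
| 13 | 29.9% | 22.6% | 7.3 |

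**Step 3: what the gap means.** In a repeat, the cystectomy subjects were drawn at random from those still failure-free, so the censoring was uninformative by construction. Censored EFS was 30.1%, 30.0% and 30.1% against a truth of 30%, and the exits-as-events figures were 28.4%, 26.1% and 22.8%. The same gap therefore appears with no bias at all. It is the difference between two endpoint definitions, and it equals the bias only if every such subject was about to fail.

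The opposite extreme is that none of them would have failed by 18 months. With no other censoring before then, EFS would be the exits-as-events figure plus k/134:

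- k = 3: 28.2 + 2.2 = 30.4%
- k = 7: 26.0 + 5.2 = 31.2%
- k = 13: 22.6 + 9.7 = 32.3%

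The censored estimate of 29.9% lies inside each range. The range runs further below it than above it.

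**Step 4: how large the assumed counts are.** About 0.45 × 134 = 60 subjects are failure-free after the first evaluation. Thirteen cystectomies without failure would be 13/60 = 22% of them, seven would be 12%, and three would be 5%.

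**Step 5: a second exit model.** Take constant hazards λ (failure) and μ (either exit) over 1.5 years. Set exp(−1.5λ) = 0.30, choose μ so that a share c of subjects exits without prior failure by 18 months, and compute exp(−1.5(λ + μ)). The result is 29.0% at c = 2%, 27.4% at 5% and 24.9% at 10%.

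Conversely, if EFS with exits as events is exactly 20%, the censored estimate is 0.20^(1 − c/0.8), that is 20.8%, 22.1% and 24.5%. In simulation (4,000 runs, log-log interval) the chance that the lower 95% limit exceeds 20% was 2.3% with no exits, then 4.0%, 7.8% and 20%. These chances are error rates only if the exits are accepted as events.

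**Step 6: the tract passages side by side.**

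- SAP 3.3.7, treatment failure: positive central cytology without evidence of tract malignancy is a failure; with such evidence it is not.
- SAP 3.3.7, EFS: tract carcinoma is censored at diagnosis.
- SAP section 8: tract disease could not be determined.
- SAP 5.2.1, rule 1: failure includes "centrally read cytology results ('High Grade Urothelial Carcinoma') that indicate treatment failure", with no mention of tract status.
- SAP section 12: Listing 16.2.8.9 covers extravesical disease evaluation.

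If tract disease goes unidentified, positive cytology defaults to failure, which is an EFS event and does not raise EFS. The passages therefore leave open how the rule is to be applied. They do not show an upward bias from it.

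**The case against.** The strongest reply is that recurrence is already captured. High-grade recurrence is a treatment failure, and SAP 3.3.7 also counts anyone discontinued for failure or recurrence. Only subjects without documented failure are censored at cystectomy, and the Introduction's remark concerns patients whose disease has recurred. This stands in part. It means that the censored group may be small and that a link to prognosis within it is plausible but not established. It does not show the link to be absent.

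The rule is also pre-specified in the protocol, and cystectomy is the event in a separate all-subject endpoint, cystectomy-free days. Both are true. But pre-specification does not make censoring uninformative, and cystectomy-free days does not re-estimate EFS.

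Three stronger readings are tempting and are not supported:

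- A reader might infer that EFS is inflated by an amount comparable with the 10 points under test. The exit counts are assumptions, only the top scenario comes near that size, and step 3 shows that the gap arises without bias.
- A reader might infer that the tract rule inflates EFS. The default to failure in SAP 3.3.7 points the other way when tract disease is not identified.
- A reader might infer that the SAP makes one cytology result a response failure and an EFS censoring. Rule 1 of SAP 5.2.1 covers results that indicate treatment failure and can be read through the 3.3.7 definition, with its tract exemption. This is an ambiguity rather than a proven contradiction.

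**Conclusion.** The point holds as a possible bias that the plan does not test. EFS is censored at two exits that may be disease-linked, and no EFS sensitivity analysis addresses either. Under the assumptions of step 2, the worst case moves 18-month EFS from about 30% to about 28%, 26% or 23% for 3, 7 or 13 cystectomies; the bias is zero if the exits are unrelated to prognosis. The true size cannot be known without the exit counts. EFS is a secondary endpoint, and the primary complete response rate does not use this censoring. On tract disease, the supportable point is that the exemption and the censoring rule need reconciling with the rest of the SAP. Label: cheap improvement.

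**What to change.** Keep the protocol rule for the main EFS table, and make three additions to the SAP.

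1. Pre-specify one sensitivity Kaplan-Meier analysis of EFS in which cystectomy without documented failure, and documented extravesical urothelial carcinoma, count as events on their dates.
2. Report the number of subjects censored for each reason, with a row for each of these two exits in the EFS censoring table of 3.3.7.
3. Reconcile the tract-disease exemption and censoring in 3.3.7 with the section 8 statement and with rule 1 of 5.2.1. State how tract disease is identified, how complete that information is, and whether the exemption applies under rule 1.

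The inputs should already exist: cystectomy dates are needed for cystectomy-free days, and Listing 16.2.8.9 covers extravesical evaluations. Given section 8, only documented tract cases can be counted, and the table should say so. The cost is one extra table and some text. The downside is that it will show an EFS figure no higher than the main one, and probably less favourable. If few subjects left by these routes, the table will show that the main estimate is robust.

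### EFS censors never-assessed subjects at first dose, so they drop out of an 18-month rate whose hypothesis covers all 134; no planned EFS analysis tests the effect

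*SAP*

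**What the plan says.** **EFS rule.** In the SAP 3.3.7 censoring table, the row "No on-study disease assessments and no death" gives the date of first dose as the censoring date. The first scheduled disease evaluation comes after the 12-week induction: cytology in Week 12 and cystoscopy from Week 13 (Protocol 10.4).

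**What stays an event.** Death before treatment discontinuation is an event. So is discontinuation for treatment failure or recurrence (SAP 3.3.7, Treatment Failure). Cystectomy and upper or lower tract disease are censored at their own dates.

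**EFS hypothesis.** SAP 3.1 says EFS "will be used to assess the treatment effect in all subjects", CIS and papillary-only together. It adds: "The total sample size of 134 subjects will provide at least 80% power to test the null hypothesis" of a 20% rate at 18 months, against 30% or more.

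**Response rule.** For complete response in Cohorts 1 and 2, SAP 5.2.1 says: "Patients who discontinue or die before Month 3 will be included in the denominator of the primary analysis". Discontinued subjects whose data are missing are non-CRs.

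**Sensitivity analyses.** The two in SAP 5.2.3 both concern complete response. SAP 5.2.5 repeats EFS in four populations but does not vary this censoring rule.

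**The concern.** A subject censored at first dose leaves the risk set before any later event. The 18-month rate is therefore estimated only from subjects who reached an assessment, and then set against a 20% figure stated for everyone.

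For CIS subjects the two efficacy rules pull apart. A subject who enters with CIS, stops during induction and is never evaluated is a non-responder in one analysis. In the other, that subject implicitly receives the average outcome of those evaluated. Being event-free at 18 months would need a clearance that was never observed, so non-informative censoring is hard to defend for this group. In the same CIS subjects, 18-month EFS could exceed 18-month complete response partly because of the rule.

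At stake is whether a statement that 18-month EFS exceeds 20% depends on how a few early leavers are handled.

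**Working it through.** **Inputs.** N = 134, null 20%, alternative 30% (SAP 3.1); two-sided alpha 0.05 (SAP 5). The share d of subjects never assessed is not given for this trial. The nearest figures are the non-evaluable shares in Protocol 7: Phase 1, 61 of 64 evaluable, so d = 3/64 = 4.7%; Phase 2, 45 of 46 evaluable, so d = 1/46 = 2.2%. A 10% share is added as an assumption.

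**1. The plan's power.** One-sample test of a proportion at 18 months with no other censoring: Φ[(0.10 − 1.96·√(0.20·0.80/134)) / √(0.30·0.70/134)] = Φ[(0.10 − 0.0677)/0.0396] = Φ(0.815) = 79.3%. This agrees closely with the stated 80%. The plan does not name its formula; an exact two-sided test gives 75.5%.

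**2. Reference with no one excluded.** The smallest count whose exact (Clopper-Pearson) 95% lower limit exceeds 20% is 37 of 134. The chance of 37 or more at a true rate of 20% is 2.1%.

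**3. Effect of the rule.** With m subjects censored at first dose, and no other censoring before 18 months, the Kaplan-Meier rate is (number event-free)/(134 − m). If no never-assessed subject is event-free and the all-subject rate is 20%, the estimate tends to 0.20/(1 − d). The chance of clearing 20% is averaged over m ~ Binomial(134, d), with the exact threshold recomputed for each 134 − m.

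| d | Expected 18-month EFS | Chance that the lower limit exceeds 20% |
|---|---|---|
| 0 | 20.0% | 2.1% |
| 2.2% | 0.20/0.978 = 20.45% | 2.8% |
| 4.7% | 0.20/0.953 = 20.99% | 4.0% |
| 10% (assumed) | 0.20/0.90 = 22.2% | 7.4% |

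Holding m fixed gives 3.3% at m = 3, 3.3% at m = 6 and 7.4% at m = 13. With a Wald limit at m = 3 there is no change (2.1%).

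**4. Weaker assumption.** If never-assessed subjects do half as well as assessed ones, the estimate is 0.20/(1 − d/2). At d = 10% that is 0.20/0.95 = 21.1%, and the chance is 3.9%.

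**5. One data set, two readings.** Take 13 never assessed and 34 event-free. Under the SAP rule, 34/121 = 28.1%, with an exact lower limit of 20.3%. Counting the 13 as failures, 34/134 = 25.4%, with a lower limit of 18.3%.

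**6. Do other planned analyses cover it?** The Evaluable population requires completed induction (SAP 4.4), and the Induction Phase Dosing Compliant population is a subset of it (SAP 4.5), so both drop most of these subjects. The Study Dosing Compliant population (SAP 4.6) does not require completed induction and may keep some, but the same censoring applies to them.

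**The case against.** A reader might infer that every early leaver is censored at first dose. The documents do not support that: on-treatment deaths and discontinuations for failure or recurrence are events, and a leaver with a recorded post-treatment evaluation counts as assessed. Protocol 10.6 asks for cystoscopy, directed biopsy and cytology 30 to 37 days after the last dose if they were not done in the prior 8 weeks, unless the subject stopped for recurrence or progression. How many leavers this covers is unclear, because SAP 3.3.7 also says that assessments are not recorded after treatment discontinuation. The table's footnote, "This censoring rule acknowledges that disease assessments were not recorded after treatment discontinuation due to an AE", does not settle it, since it belongs to the row on death after discontinuation.

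Other objections also stand:
- The contrast with the response rule covers Cohorts 1 and 2 only. Cohort 3 subjects have their papillary disease resected at screening and are not in the response analysis.
- First-dose censoring is consistent with the protocol's censoring at the last non-missing assessment (Protocol 17.5).
- SAP 5.2.5 promises a confidence interval, not a decision rule. The 20% null appears only under sample size, its derivation is not given, and the exact limit used here is the SAP's method for response, not for EFS.
- Response by visit, including 18 months, already gives a conservative view for CIS subjects.

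None of these supplies an EFS analysis showing how far the result depends on the rule.

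**Conclusion.** The point holds as a conditional one. Never-assessed subjects do not inform the 18-month EFS rate, the hypothesis is stated for all 134 subjects, and no planned EFS analysis tests the consequence. The bias is upward if these subjects do worse than assessed ones. That is plausible for CIS subjects but not shown. If leaving is unrelated to outcome, the rule costs precision and introduces no bias.

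At the earlier studies' 2% to 5% the shift is about 0.5 to 1 point, even if no leaver is event-free. It reaches 2.2 points at an assumed 10%. A reader might take the roughly 20% who stop BCG for side effects (Protocol 7) as a likely share here. That figure concerns another drug and does not describe leaving before a first evaluation, so the documents do not support using it. Nor do they support saying that EFS is inflated as a matter of fact. This is a cheap improvement to a secondary endpoint and does not call for recoding the main analysis.

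**What to change.** Leave the main EFS rule as it is. Add to SAP 5.2.5 a pre-specified mITT sensitivity analysis that counts every subject with no on-study disease assessment as an event, using the same date convention as observed post-induction failures. If there is no other censoring before 18 months, the chosen date does not alter the 18-month rate.

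Report the number of such subjects by cohort, and show the 18-month rate with its 95% confidence interval beside the main result. Any claim that EFS exceeds 20% should be qualified if it does not hold in the sensitivity analysis.

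The cost is SAP wording, one extra Kaplan-Meier run on data already collected, and a supporting EFS figure that may be slightly lower.
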